7.4.2 Stopping rules for Overall Trial

The DSMB may recommend stopping the study for the following reasons:

- The data show a clinically important risk of serious adverse effects in one or both of the treatment arms.
- It becomes clear that successful completion of the study is not feasible (e.g. there is an excess of study participant dropout, missing data, lack of recruitment etc).

7.4.2.1 *Safety-Continuous Monitoring*

Adverse Events will be continuously monitored by the investigator, clinical research associate, CRO Medical Monitor and Sponsor.

If while continuous monitoring the investigator deems an adverse event to be severe, unexpected and possibly related to phenobarbital, the investigator will report the event to NEMA within 24 hours of the event. These unanticipated adverse events will events will also be reported by the PI to the local IRB in accordance with the local IRB policies. NEMA will be responsible for reporting the unanticipated adverse events to all DSMB members within 24 hours of receiving the report, and to the FDA in an IND safety report in accordance with FDA regulations. The DSMB will determine if the adverse event changes the known risk to study participants. If the information changes the known risk to study participants, the DSMB's report regarding the change in risk will be released to all participating investigators by NEMA. The DSMB may request changes to the DSMB Charter and or potentially halt the trial.

7.4.2.2 *Safety-Interim Monitoring*

The DSMB will evaluate the study after the first 10% and 50% of randomized study participants.

Criteria to be evaluated are outlined in detail in the committee charter.

8 Study Assessments and Procedures

8.1 Efficacy Assessments

8.1.1 Seizure Burden

8.1.1.1 *Total Seizure Burden*

Total Seizure Burden summarizes the duration of all seizures on the cvEEG recording for each study participant individually and is measured in minutes.

At minimum, the start and end time of each seizure will be recorded in the case report forms.

8.1.1.2 *Maximum Seizure Burden*

The Maximum Seizure Burden is defined as the maximum hourly seizure burden with the cvEEG recording and is measured in minutes per hour.

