3.2.2 Secondary Endpoints

- Percent of neonates who do not require additional seizure treatment after 2 hours of the first dose of phenobarbital.
- Percent of neonates who do not require additional seizure treatment after the second dose of phenobarbital within the first 24 hours of treatment.
- Seizure burden over 24 hours following initial administration of the phenobarbital injection.
- Seizure burden over 48 hours following initial administration of the phenobarbital injection.
- Percent of neonates requiring alternative anticonvulsive therapy for the management of seizures at 24 and 48 hours.
- Time period between the first dose and second dose of intravenous phenobarbital in neonates randomized.
- Time period between the second dose of intravenous phenobarbital and alternative anticonvulsant treatment in neonates
- Time period between the first dose of intravenous phenobarbital and administration of an alternative anticonvulsant treatment in neonates randomized.

3.2.2.1 *Justification for Secondary Endpoints*

Reduction in seizure burden, seizure recurrence and administration of rescue ASDs have been identified as reliable outcomes to assess efficacy of antiepileptic drugs in late stage drug trials (22).

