If seizures persist (≥ 30 sec/h of seizure activity) 60 minutes following the start of the initial dose of phenobarbital, neonates receiving an initial dose of 20 mg/kg will receive an additional 20 mg/kg dose. Neonates receiving an initial dose of 40 mg/kg will receive an additional 10 mg/kg dose. Administration of this second loading dose is required to be within 2 hours of recognition of qualifying seizure burden (≥ 30 sec/h). The time period between the first and second dose of study treatment will be determined by the principal investigator or site designee (recommended to be a pediatric neurologist and/or neurophysiologist) review of the cvEEG, but must be at least 30 minutes after infusion is completed and no more than 24 hours after the first dose of study treatment (22).

If the seizure activity continues (≥ 30 sec/h) is still not resolved, study participants may receive a second-line alternative anticonvulsant therapy per institutional protocol. In each treatment arm, the second-line anticonvulsant therapy will be confirmed by the principal investigator or site designee (recommended to be a pediatric neurologist and/or neurophysiologist) and recorded in the study documentation as a concomitant medication.

All phenobarbital treatment doses will be prepared by the unblinded investigational pharmacist. The investigational pharmacist will be unblinded (have access to the treatment arm labels) and will not be involved in the assessment or medical management of the neonate. All other study personnel will be blinded to the first and second phenobarbital dose treatment. Each study treatment arm will be prepared in the same total volume of administration and administered over a **30-minute infusion** in order to maintain the study blind.

Throughout the Treatment Period the neonate will be continuously monitored by cvEEG, vital signs will be recorded, clinical seizure assessment will be recorded, and blood samples will be collected for laboratory safety monitoring and phenobarbital plasma concentrations according to the schedule of activities (Section 1.3). cvEEG monitoring will continue throughout the Treatment

Period and will be discontinued at end of Follow-up Period or upon entering Open Label Extension Period.

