8.2.8 Continuous Video EEG Monitoring

Continuous video-EEG (cvEEG) monitoring is the gold standard for neonatal seizure detection and quantification and should be used whenever available for seizure detection and differential diagnosis of abnormal appearing, paroxysmal clinical events (25). It is the ideal tool to measure the exact number and duration of seizures, their site(s) of onset and spatial patterns of migration. Multichannel (minimum 8-20 channels) cvEEG monitoring is required for accurate detection of seizures to determine drug response (26).

The following are cvEEG reading **recommendations** during the Screening and Treatment Period for the site neurophysiologist or site designee:

- Review first hour of cvEEG recording as soon as possible.
- If not sure if a pattern is a seizure or study participant does not have 30 seconds/hour seizure burden, review every hour for up to 6 hours followed by every 2 hours for up to 4 hours and then every 4 hours.
- If runs of spike/sharp wave discharges or focal discharges, review every 2 hours for up to 6 hours and then review every 4 hours.
- For any other EEG background/pattern- every 4 hour (if normal not to have to wake up midnight to 6 AM).
- Shortly after reports of suspicious clinical event or 1 hour after start of a therapeutic intervention to evaluate for treatment response (assumes 30-minute infusion).

The following are cvEEG reading recommendations during the Follow-up Period and Open Label Maintenance Period:

- Site is to follow their cvEEG reading standard of practice.

It is also **recommended** that the cvEEG technologist or site designee should remain at the monitor for the first hour of recording to ensure a high-quality recording and to make note of relevant clinical signs. Thereafter, the cvEEG technologist or site designee should re-evaluate the quality of the cvEEG recording frequently and adjust recording leads as required by site's standard of practice. It is also **recommended** that the bedside research staff evaluate the quality of the recording periodically and should contact the technologist or designee if the tracing is suboptimal.

cvEEG recording and monitoring will start at time of informed consent or when study participant is hooked up (whichever is latest) and continue up to 48 hours from start time of first phenobarbital dose. cvEEG recording and monitoring after 48 hours is not required per this protocol and will follow site's standard of practice.

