Skin assessments as required by institutional standard operating procedures will be allowed. It is recommended that the amount of time the leads are off the study participant are minimized.

At minimum, the entire EEG recording will need to be backed up and archived for the study. Details regarding data transfer for the cvEEG recordings and video clippings are described in the Operational Procedure Manual.

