3.7.2. Secondary outcomes

Efficacy

- Percent of neonates who do not require additional seizure treatment after 2 hours of the first dose of phenobarbital.

CONFIDENTIAL

- Percent of neonates who do not require additional seizure treatment after the second dose of phenobarbital within the first 24 hours of treatment.
- Seizure burden over 24 hours following initial administration of the phenobarbital injection.
- Seizure burden over 48 hours following initial administration of the phenobarbital injection.
- Percent of neonates requiring alternative anticonvulsive therapy for the management of seizures at 24 and 48 hours.
- Time period between the first dose and second dose of intravenous phenobarbital in neonates randomized.
- Time period between the second dose of intravenous phenobarbital and alternative anticonvulsant treatment in neonates
- Time period between the first dose of intravenous phenobarbital and administration of an alternative anticonvulsant treatment in neonates randomized.

Safety

The following safety assessments will be performed during the study:

- Type, incidence, and severity of adverse events
- Physical examination
- Vital signs (blood pressure [arterial line], respiration rate, pulse rate, oxygen saturation and temperature)
- Clinical laboratory tests (hematology, serum chemistry)

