5.5.3. Other Outcomes (e.g. Safety, secondary outcomes etc.)

No imputation will be performed

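### Seizure burden over 24 and 48 hours is raw minutes on whatever EEG was recorded, so unrecorded time counts as seizure-free

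*Protocol*

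**What the plan says.** Protocol 8.1.1 defines two measures. The total: "Total Seizure Burden summarizes the duration of all seizures on the cvEEG recording for each study participant individually and is measured in minutes". The maximum: "The Maximum Seizure Burden is defined as the maximum hourly seizure burden with the cvEEG recording and is measured in minutes per hour". Only the second is expressed per hour, and neither document ties it to the windowed endpoints. Those endpoints are "Seizure burden over 24 hours following initial administration of the phenobarbital injection" (Protocol 3.2.2) and "Seizure burden over 48 hours following initial administration of the phenobarbital injection" (SAP 3.7.2).

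On recording, Protocol 8.2.8 has cvEEG "continue up to 48 hours from start time of first phenobarbital dose", with no minimum. It permits skin checks and says of interruptions: "It is recommended that the amount of time the leads are off the study participant are minimized". It also requires the whole recording to be archived.

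On incomplete data, Protocol 9.4.2 counts withdrawal within 24 hours as failure on the primary endpoint and leaves dropouts on other endpoints to the SAP. For secondary outcomes SAP 5.5.3 says only: "No imputation will be performed". SAP 7.2 uses the ITT population. SAP 7.2.2 fits a Gaussian, identity-link model with treatment, HIE and seizure burden group, and has no offset or weight for recorded time.

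**The concern.** A sum of minutes over a fixed window is comparable between neonates only if the window was recorded for each of them. Here any neonate with some EEG has a non-missing total, so the no-imputation rule does not act on it, and the lost hours add zero minutes.

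Incomplete recording is foreseeable. Leads may come off, recording runs only up to a limit, and neonates may be withdrawn. Protocol 4.1 says cvEEG "will be discontinued at end of Follow-up Period or upon entering Open Label Extension Period", whereas footnote 4 of the open-label schedule (1.3.1) has it carry on until 48 hours. Open-label entry is possible from 24 hours after T0 (4.1.5), so under the wording of 4.1 the 48-hour endpoint could lose up to half its window. Entry depends on needing maintenance phenobarbital, so that loss could be related to outcome.

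At stake is whether a lower mean burden in one arm reflects fewer seizures or less EEG. As planned, the analysis cannot separate the two.

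**Working it through.** **Inputs.** The windows (24 and 48 hours) come from Protocol 3.2.2. The documents give no mean burden, SD, time course or amount of lost recording, so every burden rate and loss pattern below is an assumption. The only related planning figure is the sample size for the primary endpoint. It reproduces: 70% against 50%, two-sided alpha 0.05, 80% power and pooled variance give 93 per group, and 186/0.95 = 195.8, so 196. It does not bear on burden.

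**Constant rate r (min/h), window W, recording stops at t.** Recorded minutes are r·t and the full total is r·W, so the shortfall is 1 − t/W whatever r is. At 18 of 24 h: 1 − 18/24 = 25%. At 24 of 48 h: 50%.

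**Burden halving every h hours.** The share captured is f = (1 − 2^(−t/h)) / (1 − 2^(−W/h)). A single rate per neonate (minutes divided by recorded hours), relative to the true window average, equals f/(t/W). With W = 24 and h = 6 the denominator of f is 1 − 1/16 = 0.9375:

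| Stop at | Raw minutes, constant rate | Raw minutes, 6-h half-life | One rate per neonate, 6-h half-life |
|---|---|---|---|
| 18 h | 25% low | 0.875/0.9375 = 0.933, 7% low | 0.933/0.75 = 1.24, 24% high |
| 12 h | 50% low | 0.75/0.9375 = 0.80, 20% low | 0.80/0.50 = 1.60, 60% high |
| 6 h | 75% low | 0.5/0.9375 = 0.533, 47% low | 0.533/0.25 = 2.13, 113% high |

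With a 12-h half-life and a stop at 12 h, raw minutes are 33% low and the single rate 33% high. For the 48-h window with a stop at 24 h, f is 0.9375/0.9961 = 0.94 (6% low) with a 6-h half-life and 0.75/0.9375 = 0.80 (20% low) with a 12-h half-life.

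**Between arms.** Take equal true burden, with 5% of one arm and 15% of the other stopping at 12 of 24 h. The spurious difference is (0.15 − 0.05) × shortfall: 0.10 × 50% = 5% of the mean at a constant rate, 0.10 × 20% = 2% with a 6-h half-life. At an assumed 2 min/h, the 5% is 46.8 against 44.4 minutes, or 2.4 of 48. Equal loss with equal true burden gives no difference.

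**Check of the remedy.** With a 6-h half-life, the four 6-hour bins hold 53.3%, 26.7%, 13.3% and 6.7% of the 24-hour burden. Let 15% of an arm stop at 12 h. Mean raw minutes are 0.85 × 1 + 0.15 × 0.80 = 0.97 of the truth. The mean of single rates is 0.85 × 1 + 0.15 × 1.60 = 1.09. Arm-level bin rates, with the last two bins estimated from the 85% still recorded, sum to 1.00. This holds if those lost resemble those still recorded in the same arm and bin.

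**The case against.** The strongest reply is that the plan never says how a partial recording is scored. The no-imputation rule also fits setting an incomplete window to missing, and the SAP does not state that burden in the endpoints means the total defined in 8.1.1. That is fair, and the point is therefore put as the literal reading. The alternative does not rescue the plan: it would exclude neonates selectively, against the ITT rule, and it is not stated either.

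A reader might infer that neonates who die receive a falsely low burden. The documents do not support that. No seizures follow death, so the minutes are complete. Death is an intercurrent event with no stated strategy, and an early death would score as a good result. Protocol 7.4.1.2 lists death among expected events, although 5.2 excludes neonates whose death appears imminent.

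A reader might also infer that the high-dose arm is favoured. Nothing in the documents shows which arm would lose more recording, or how much. The only attrition figure is about 5%, and it concerns the primary endpoint.

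A third tempting step is to divide each neonate's minutes by recorded hours. That suits scattered gaps, but the table shows that it overstates burden after early truncation when burden is front-loaded. Making a minimum recorded time a condition of the main analysis would drop losses that may be related to outcome.

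Some safeguards do stand. Stopping study drug does not end study procedures (7.1), non-responders stay under observation (7.4.1.1), and frequent checks of recording quality are recommended (8.2.8). These reduce loss but do not say how to score it. The SAP also treats secondary outcomes as exploratory (5.6).

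**Conclusion.** The concern holds for the two burden endpoints. As written, unrecorded time is counted as seizure-free, and the analysis has no means of allowing for it. For a neonate whose recording stops at 18 of 24 hours the shortfall is 7% to 25%, over assumptions from a 6-hour half-life to a constant rate. At 24 of 48 hours it is 6% to 50%. Between arms, 5% against 15% stopping at 12 of 24 hours would create a 2% to 5% difference on the same assumptions. These figures suppose that seizures would have occurred in the lost time. Whether loss will differ by arm, and in which direction, cannot be known from the documents. The primary endpoint has its own failure rule and is unaffected, as is the sample size. This should be corrected before unblinding, but the trial's main conclusion does not depend on it.

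**What to change.** In the SAP:

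- State that the endpoints use Total Seizure Burden. Derive interpretable recorded time from the archived EEG and tabulate it by arm.
- Compute seizure minutes and recorded hours in fixed bins after T0, within 0–24 h and 24–48 h. Analyse burden with recorded time as the exposure within bin, for example bin-specific rates summed over the window. Do not use one crude rate per neonate.
- Keep every ITT neonate with any recording in the main analysis. Use raw minutes, and a subset with a pre-set minimum recorded time, as sensitivity analyses.
- Treat death as an intercurrent event, not as missing EEG, with its strategy stated in advance. One option is burden while alive with deaths shown by arm, plus a sensitivity analysis ranking death as the worst outcome.

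Two pairs of protocol passages must be reconciled, because they determine what burden can be computed. Section 4.1 and footnote 4 of 1.3.1 disagree on whether cvEEG stops at open-label entry. Section 8.1.1 wants the onset and offset of every seizure in the case report form, whereas 8.1.4 asks for all seizures only in the first 2 hours and afterwards only those that prompted treatment. A burden derived from the form under 8.1.4 could be undercounted for everyone.

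The cost is SAP wording, extraction of recording times from files already kept, and slightly more analysis work. The result is less direct than total minutes, which can still be listed.

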8.1.2 Seizure Recurrence

The recurrence of seizures is measured by total seizure burden from the end of the defined response period until 24 h after study drug administration. If the study participant continues in the open-label period, seizure recurrence will be evaluated every 24 hours until discharge. This is contingent on maintenance of therapeutic levels of study drug.

8.1.3 Seizure Period

Seizure period is calculated as the time from the onset of the first electrographic seizure to the offset of the last electrographic seizure.

8.1.4 Seizure Documentation

The start and end time of seizures will be recorded in the case report forms based on the following guidelines:

- All seizures within the first 2 hours from the start of the first dose of study drug.
- If a second dose of study drug is given, start time of seizure that prompted a second dose will be recorded as well as the stop time of the seizure.
- If need to give a second line seizure medication, document start time for the seizure that prompted giving the second line seizure medication as well as the stop time of the seizure.
- If seizures continue, for each additional seizure medication administered, document start time for the seizure that prompted giving the seizure medication as well as the seizure stop times.

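### Protocol 8.1.4 logs every seizure only up to 2 h and then only treatment-prompting ones, against 8.1.1.1; a CRF kept that way cannot give valid 24-h and 48-h seizure burden

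*Protocol*

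**What the plan says.** Protocol 8.1.1.1 defines total seizure burden as the summed duration, in minutes, of all seizures on the cvEEG. On data capture it says: "At minimum, the start and end time of each seizure will be recorded in the case report forms". It sets no time limit.

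Protocol 8.1.4 covers the same CRF entries. Its first item is "All seizures within the first 2 hours from the start of the first dose of study drug". The remaining items ask for the timing of the seizure that led to a second study dose, to a second-line drug, and to each later drug. Seizures before the first dose are not listed.

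The secondary endpoints in Protocol 3.2.2, repeated in SAP 3.7.2, include burden over 24 h and "Seizure burden over 48 hours following initial administration of the phenobarbital injection". Protocol 8.1.2 describes recurrence as "measured by total seizure burden from the end of the defined response period until 24 h after study drug administration". Protocol 8.1.3 defines seizure period as "the time from the onset of the first electrographic seizure to the offset of the last electrographic seizure". Pre-treatment seizure burden is a covariate (Protocol 9.4.2, SAP 5.3) and a subgroup variable (Protocol 9.4.7, SAP 5.4).

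On the EEG itself, Protocol 8.2.8 says "At minimum, the entire EEG recording will need to be backed up and archived for the study". For reading in the Follow-up and open-label periods it says "Site is to follow their cvEEG reading standard of practice". Protocol 4.1 says cvEEG continues throughout the Treatment "Period and will be discontinued at end of Follow-up Period or upon entering Open Label Extension Period". In contrast, footnote 5 of Section 1.3, footnote 4 of Section 1.3.1 and Section 8.2.8 run the recording to 48 h after the first dose.

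**The concern.** Two current sections give different rules for the same CRF data, and the narrower one does not supply what the burden endpoints need. Three consequences follow.

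- **Capture depends on outcome.** Under 8.1.4, a seizure after 2 h is entered only if it prompted medication. Re-treatment is what the primary endpoint compares, so if the arms differ on it, the arm difference in CRF burden is mixed up with treatment use. SAP 5.5.3 does not impute secondary outcomes. In any case an unentered seizure would not appear as missing; it would count as zero minutes.
- **Sites may differ.** If some follow 8.1.1.1 and others 8.1.4, burden is not comparable across sites.
- **Related measures are affected.** Recurrence to 24 h needs every seizure. Seizure period needs the first onset and the last offset, and 8.1.4 secures neither. Pre-treatment burden needs pre-dose seizures. The high/low burden factor in the SAP primary model is a separate, undefined variable that may be captured at randomisation, so it is not counted here.

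**Working it through.** **Inputs.** Full-entry window of 2 h from the start of the first dose (Protocol 8.1.4). Endpoint windows of 24 and 48 h (3.2.2). Treatment trigger of 30 s/h (4.1). Planning rates of 50% (low dose) and 70% (high dose) controlled, 93 completers per group, 196 randomised (9.2).

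**The plan's own figures.** The documents give no expected burden, SD or power for burden, so there is none to reproduce. The sample size does reproduce: a two-sided pooled comparison of 0.50 with 0.70 at alpha 0.05 and 80% power gives 93 per group, and 186/0.95 = 195.8, rounded up to 196, or 98 per arm.

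**1. Share of each window fully captured under 8.1.4.** 2/24 = 8.3%; 2/48 = 4.2%. These are shares of time, not of burden.

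**2. Who can have an entry between 2 and 24 h.** Only a re-treated neonate can. Low dose: 1 − 0.50 = 0.50, and 98 × 0.50 = 49. High dose: 1 − 0.70 = 0.30, and 98 × 0.30 = 29.4. These are upper limits, because some re-treatment will be prompted by seizures within the first 2 h. On the 93 completers they become 46.5 and 27.9.

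**3. Burden that can go unentered without reaching the trigger.** The formula is hours after 2 h × assumed steady rate. The rates are assumptions, not from the documents.

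| Assumed rate | 2–24 h (22 h) | 2–48 h (46 h) |
|---|---|---|
| 5 s/h | 110 s = 1.8 min | 230 s = 3.8 min |
| 15 s/h | 330 s = 5.5 min | 690 s = 11.5 min |
| 29 s/h | 638 s = 10.6 min | 1,334 s = 22.2 min |

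Such a neonate can be a primary-endpoint success with none of these minutes in the CRF. Above the trigger the loss has no such ceiling, because only the prompting seizure is entered.

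**4. What happens to the measure above the trigger.** Assume 5 min of seizures in the first 2 h, later seizures of 1 min each at r per hour, and at most three prompting seizures entered. None of these figures is from the documents. Expected true burden is 5 + 22r at 24 h and 5 + 46r at 48 h; the CRF holds at most 5 + 3 = 8 min.

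- r = 0.25: 10.5 min at 24 h and 16.5 min at 48 h.
- r = 1: 27 min at 24 h and 51 min at 48 h.

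A simulation on these assumptions gave CRF means of 7.9 to 8.0 min throughout. The recorded value hardly moves while the true value more than doubles or triples.

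**5. Whether another source closes the gap.** The EEG is archived, but neither document describes scoring it for burden, and the SAP names no data source or derivation. Protocol 8.2.8 and 10.1.10.1 refer to the Operational Procedure Manual for transfer of recordings only. From 24 to 48 h, reading follows site practice and Protocol 4.1 asks for seizure activity only in general terms.

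**6. The recording window.** Maintenance cannot start before 24 h (Protocol 4.1.5), so the Section 4.1 sentence ending cvEEG on entry to the extension leaves the 24-h endpoint alone. It would cut the 48-h recording short for neonates who enter between 24 and 48 h.

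**The case against.** The best defence is that 8.1.1.1 is worded as a floor, while 8.1.4 calls its list guidelines and never says that other seizures are left out. On that reading 8.1.4 merely links seizures to treatments. But an explicit 2-h limit has no purpose if every seizure is entered anyway, and a site could reasonably follow 8.1.4 as written.

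Second, the Operational Procedure Manual or CRF guide may contain a reading arrangement, and 8.2.8 does address screening and treatment-period reading to the site neurophysiologist or designee. That is fair as far as it goes. Those reading intervals are recommendations for managing treatment; they do not assign scoring of every seizure for an endpoint.

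Third, the figures do not measure bias between arms. This stands. Nor can the direction be stated: neonates not re-treated lose all seizures after 2 h, while re-treated neonates lose all but the prompting ones.

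Fourth, SAP 5.6 treats secondary analyses as exploratory, and recurrence and seizure period are not listed endpoints. Both are correct and limit the weight of the point. They do not make outcome-dependent capture acceptable for two named endpoints. On the recording window, footnote 4 of Section 1.3.1 covers the extension case directly, so that part needs one sentence reconciled.

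**Conclusion.** The concern holds. Sections 8.1.1.1 and 8.1.4 conflict, and a CRF kept by 8.1.4 cannot validly give the 24-h and 48-h burden endpoints: complete entry covers 8.3% and 4.2% of the windows, and later entry depends on re-treatment, with at most about 49 versus 29 of 98 neonates per arm able to have any entry from 2 to 24 h at the planning rates. The minutes lost rest on assumed seizure rates and are illustrations. The conclusion assumes that at least some sites follow 8.1.4 and that no unseen manual sets a burden reading. The treatment-based primary endpoint, its sample size and its alpha are not affected, and the data remain recoverable from the archive. It should be fixed, but it does not threaten the main result.

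**What to change.** 1. Bring 8.1.4 into line with 8.1.1.1: enter the onset and offset of every electrographic seizure from the pre-dose qualifying period to 48 h after the start of the first dose, taken from the cvEEG already recorded and archived. State who reads it, preferably blinded to arm.
2. Reconcile the Section 4.1 sentence with footnote 5 of Section 1.3, footnote 4 of Section 1.3.1 and Section 8.2.8, so that every randomised neonate has the same recording window.
3. In the SAP, name the data source and derivation for burden and the handling of recording gaps. Where recordings are still short, report burden per recorded hour as a supporting analysis only, because the seizure rate may change over time.

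**Cost.** Protocol, SAP and CRF-guideline wording, and more seizure lines per neonate. Reading for the study from 24 to 48 h is at most 196 × 24 = 4,704 EEG-hours. Marking every seizure from 2 to 24 h covers up to 196 × 22 = 4,312 further hours, which 8.1.1.1 already demands. Pre-dose reading is additional. No new procedure on the neonate is needed.
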